### **6.6.3. Processing Speed**

Processing speed, a potential contributor or mediator of both memory and executive function, will be assessed using reaction time subtests from the **California Computerized Assessment Package** (CALCAP-RT; Miller, 2013).

The **CALCAP** is a comprehensive tool for assessing reaction time, speed of information processing, rapid visual scanning, form discrimination, brief memory and divided attention. We plan on administering the **abbreviated version**, which consists of 4 subtests that take approximately 8-10 minutes. All tasks are given on a computer. The 4 subtests are described below.

- Simple Reaction Time. Subjects are asked to press a key as soon as they see anything at all on the screen. This procedure provides a basal measure of reaction time.
- Choice Reaction Time for Single Digits. Subjects are asked to press a key as soon as they see a specific number such as '7', otherwise they are to do nothing. This procedure adds a simple element of memory to the task.
- Serial Pattern Matching 1 (Sequential Reaction Time 1). Subjects are asked to press a key only when they see two of the same number in sequence, for example, if they see the number '3' followed by a second occurrence of the number '3'. This procedure adds a more complex element of memory since the subject must keep in mind the last number that was seen.
- Serial Pattern Matching 2 (Sequential Reaction Time 2). Subjects are asked to press a key only when they see two numbers in sequence (increasing order). For example, if they see the number '3' followed by the number '4', the number '6' followed by '7' and so on.

### **6.6.4 Mood Measures [Emotion module of NIH Toolbox, STAI, POMS, BDI-II, AS]**

**6.6.4a. Description of NIH Toolbox Emotion Module** (Salsman et al., 2013). The NIH Toolbox for the Assessment of Neurological and Behavioral Function ([www.nihtoolbox.org](http://www.nihtoolbox.org)) is a standardized set of Web-based measures developed through a contract initiated by the NIH Blueprint for Neuroscience Research ([Gershon et al., 2013](http://www.nihtoolbox.org)). It contains four modules: Motor, Sensation, Cognition, and Emotion.

This study will use the Emotion module. It is a 12 to 22 minute computer administered, self-report measure of emotional health and psychological function. It surveys positive and negative emotions such as joy, sorrow, fear, etc.. Questions consist of likert-type items that are rated by a participant. The module consists of 4 scales: Psychological Well Being, Negative Affect, Social Relationships, and Stress& Self Efficacy. Each is described below. The dependent variable is the T score from each measure. The first two scales are the co-primary outcomes and the latter are the secondary outcomes:

1. Psychological well-being (co-primary outcome). Subscales making up this domain include: general life satisfaction, meaning and purpose, and positive affect. Participants rate statements such as “I

am satisfied with my life", "I value my activities", and "there is not enough purpose in my life". There are a total of 76 items on the Psychological Wellbeing scale.

2. Negative affect (co-primary outcome; subscales making up this domain include anger, fear, and sadness). Participants rate statements such as "I feel worthless" and "I felt envious of others". A total of 89 items are given on the Negative Affect scale.
3. Social Relationships (exploratory outcome, subscales making up this domain include social support, companions, social distress, and positive social development). Participants rate statements such as "people in my life act as if they don't care about me" and "people don't listen when I ask for help". A total of 26 items will be given on the Social Relationships scale.
4. Stress and Self-efficacy (exploratory outcome; subscales making up this domain include: perceived stress and self-efficacy). Participants rate statements and questions such as "I can handle whatever comes my way" and "how often in the past month did you feel nervous and 'stressed'". A total of 20 items will be given on the Stress and Self-efficacy domain.

**6.6.4b. Description of State Trait Anxiety Inventory** (STAI; Spielberger, 1983a; 1983b; 1989). The STAI is a 40-item questionnaire that is used to assess current (state) and general (trait) levels of anxiety. Higher scores represent higher levels of anxiety, or feelings of worry, tensions, and stress. Items on the questionnaire include ratings of statements such as "I feel calm", "I am jittery", and "I feel nervous". The STAI has been used extensively in clinical and research settings and displays a test-retest reliability of 0.31 to 0.86 and internal consistency alpha coefficients of 0.86 to 0.95 (Spielberger et al., 1983a). Further, this measure shows high convergent validity with other measures of anxiety (0.72 to 0.86; Spielberger et al. 1989).

**6.6.4c. Description of Profile of Mood States, short form** (POMS, Curran et al., 1995). This is a 30 item self- report questionnaire of mood states such as "discouraged", "grouchy", "vigorous", and "efficient". The short form version of the POMS is easy to administer, and yields information about transient current mood states. The measure is grouped into subscales including tension, depression, anger, fatigue, and vigor. Test-retest reliability ranges from 0.65 to 0.74, internal consistency is 0.93, and the test also features high degrees of construct validity (Curran et al., 1995).

**6.6.4d. Description of Beck Depression Inventory-II** (BDI-II; Beck et al., 1996). This is a 21 item self-report questionnaire of symptoms of depression such as sadness, self-criticalness, loss of interest, or somatic changes such as insomnia or increased sleep, increased or decreased appetite, and low energy. This questionnaire allows one to characterize levels of depression as mild, moderate, or severe, depending on the total score. The BDI-II has strong convergent validity, internal consistency ( $\alpha=.91$ ) and test-retest reliability ( $r=.93$ ) and has been used extensively in clinical and psychological research.

**6.6.4f. Description of Apathy Scale** (AS, Marin et al., 1991). This is a 14 item self-report questionnaire that assesses for symptoms of motivation, drive, and initiative. Participants answer questions on a 5 point likert scale ranging from 0 to 4. The AS has been subgrouped into components reflecting cognitive, affective, and behavioral components of apathy. Test-retest reliability is strong, and the AS has strong convergent validity with real world indicators of behavior (Ferencz et al., 2012).

## **6.6.5 Other Measures**

**6.6.5a. Placebo Control Questionnaire** (PCQ): This is a 4-item questionnaire that is given after the end of the 2-week intervention. It asks questions regarding which group (real, sham) the participant believes they were assigned.

**6.6.5b. Adverse Events Log (AE).** This is a standard open ended questionnaire regarding symptoms or adverse events that the participant has experienced since beginning the intervention. This will be assessed at the end of each intervention session and will prompt for symptoms the participant may have experienced during the session and/or since the previous intervention session. It queries for severity, how long the symptoms last, and whether (if known) the symptom might be related to the intervention. This will also be assessed during the followup session.

**6.6.5c. Fitzpatrick Skin-Type Questionnaire** (Fitzpatrick, 1986): This is a 10 item self-report form where participants indicate hair, eye, and skin color, as well as rate burning and tanning to sun exposure. This information is being obtained because skin and hair pigmentation may impact the penetrance of infrared light through the skin and scalp. This scale is often used in dermatology and will be used to as a covariate in statistical analyses.

**6.6.5d. Cognitive Change Index (CCI)** On this 20 item questionnaire, participants rate changes in their own thinking and memory. They use a 5 point Likert scale that goes from 1 (no problem/normal ability) to 5 (much worse/severe problem). Domains that are covered include multi-tasking, learning new things, recalling old memories, thinking quickly, retrieving names, etc. This questionnaire will be given before and after the intervention to assess perceived changes.

**6.6.5e. Expectancy Questionnaire:** This measure is given prior to the intervention and asks participants to rate their expectations about changes they anticipate will change as a result of the intervention.

**6.6.5f. Followup Questionnaire:** This measure is given after the intervention. It asks participants to rate the extent that they experienced changes in particular cognitive and functional domains

**6.6.5g. Pittsburgh Sleep Quality Index:** This is well-known and well-validated sleep scale for detecting insomnia and sleep quality. It will be given before and after the intervention.

**6.6.5h. Fatigue Severity Scale (FSS):** This is standard self-report questionnaire that measures degree of fatigue that an individual experiences. It will be given before and after the intervention.

**6.6.5i. Pain Rating Scale.** This is analogue rating scale where participants rates the current severity of any ongoing pain.

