Grooved Pegboard (PD only)			X			X
Walking-Balance (PD only)			X			X
BDI-II			X			X
STAI			X			X
Apathy Scale			X			X
NIH Toolbox Emotion			X			X
POMS			X		X	X
Fatigue Severity Scale			X			X
Pittsburgh Sleep Quality Index			X			X
Pain Rating Scale			X			X
Adverse Events Log					X	X
Expectation Quest		X				
Placebo Control Quest						X

\*MRI, only a subset of participants will be asked to undergo pre and post-MRI; these will be screened for eligibility using a standard MRI screener\*\*. MoCA=Montreal Cognitive Assessment; HVLT-R=Hopkins Verbal Learning Test – Revised; WMS-III LM = Wechsler Memory Scale, Logical Memory subtest; Charlson = Charleson Comorbidity Index; WTAR=Wechsler Test of Adult Reading; JLO = Judgement of Line Orientation; Skin type Questionnaire =Fitzpatrick Skin-Type Questionnaire; AVT=Auditory Verbal Learning Test; MST = Mneumonic Similarity Test; CalCap = California Computerized Assessment Package; UPDRS = Unified Parkinson Disease Rating Scale; BDI-II=Beck Depression Inventory, 2nd edition; STAI=State Trait Anxiety Inventory; POMS=Profile of Mood States, Short Form; PCQ=Placebo Control Questionnaire; ; Daily journal = completed by participant for recording time of daily intranasal treatment.

- Note that individuals with Parkinson disease will receive the Unified Parkinson Disease Rating Scale, Grooved Pegboard Test, and Gait Rite analysis before and after intervention. Other participants will not.

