## 10. Data Safety Monitoring Plan

The PI, Co-Is, or project coordinator will meet with each participant to review the adverse events questionnaires and assess for negative effects on the safety of participants. This questionnaire will be reviewed after every intervention session and at the follow up evaluation. As this intervention involves an infrared lamp that has been FDA approved as a non-significant risk, we do not anticipate adverse events or side effects. However, should a participant experience any adverse event of sufficient concern at any point during the intervention or at follow up, we will report to the IRB as directed. The PI and/or project coordinator will send via email a monthly report to the investigative team indicating the nature of any adverse events. If there are no reported adverse events, then an email summary will not be sent that month. The PI will take primary responsibility of the Data Safety and Monitoring Plan.

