## **12. Possible Discomforts and Risks**

The risks are minimal for individuals who participate in this study. Light is applied using light emitting diodes, which do not present as a serious ocular hazard. Near infrared light is non-thermal, painless, and was designated as a non-significant risk by the FDA in 2003. It is estimated that approximately  $6 \text{ J/cm}^2$  is expected to reach the cortex with each daily treatment. At this energy level, the MedX MCT502 and Vielight 810 accessories do not cause tissue damage or physical damage.. As part of normal operation, the LED clusters may warm up during the application of light. The temperature of the MedX Clusters does not exceed  $45^\circ \text{ C}$  ( $113^\circ \text{ F}$ ) during operation.

There are four types of potential risks for participants in this study.

First, the completion of various screening and cognitive probes could potentially become boring or tiresome. To minimize fatigue associated with completion of screening and baseline tasks, participants will be given frequent breaks and the opportunity to rest.

Second, there is potential risk of loss of confidentiality. This will be minimized through assigning all data collection instruments a unique code without individual identifying information. All HIPAA regulations pertaining to protection of participants and eliminating identification will be followed.

Third, a subset of participants will undergo MRI. This is perhaps poses the greatest discomfort. Because the MRI scanner has a strong magnet, individuals with metal implanted in their body cannot participate. The scanner produces a loud hammering noise, which has produced hearing loss in a very small number of participants. All participants are provided with ear protection while in the scanner. There is not much room in the scanner and it can be uncomfortable to remain still for the scan. Individuals with known claustrophobia will be excluded from participating.

Fourth, it is also possible that incidental findings may emerge on the MRI. In this situation, the participant will be informed and recommendation/referrals will be made with the participant's permission. This could include provision of information to the participant's primary care physician and/or referral to another health care professional for followup.

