For individuals with Parkinson disease, there is an additional potential discomfort. The PD participants may experience some increase in their symptoms (i.e., increased slowness, tremor, rigidity) when they are tested during the "off medication" state. This is similar to what occurs during their routine clinical evaluation at the Movement Disorders Clinic, when they are asked to come to their clinic appointment after being off their Parkinson medication overnight. For our research study, care will be taken to ensure that the Parkinson patients are transported by wheelchair when necessary and that they are accompanied by a member of the study team. They will be told that if they become too uncomfortable, then they should go ahead and take their medication.

It is possible that there are unknown risks for participating in this study. Individuals will be asked about side effects at each visit and encouraged to share information about subjective changes.

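### The protocol says participants will be asked about side effects at each visit, but its Adverse Events Log starts with the intervention and ends at follow-up, leaving out the Parkinson off-medication baseline and the pre-intervention MRI.

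*Protocol*

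**What the plan says.** **When the log is used.** Section 6.6.5b describes an open-ended form covering "symptoms or adverse events that the participant has experienced since beginning the intervention". On timing it says "This will be assessed at the end of each intervention session" and then "This will also be assessed during the followup session". In Table 2 (Section 6.8) the row "Adverse Events Log" is marked under Intervention and Follow-up only. Screening, Baseline, Pre-MRI and Post-MRI carry no mark.

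**When it is reviewed and reported.** Section 10 states: "This questionnaire will be reviewed after every intervention session and at the follow up evaluation". Its reporting sentence has the same limits, covering an event of concern "at any point during the intervention or at follow up, we will report to the IRB as directed".

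**What participants are told to expect.** Section 12 tentatively ranks MRI as the most uncomfortable part of the study and says of scanner noise "which has produced hearing loss in a very small number of participants". It adds a separate discomfort for Parkinson participants, a worsening of motor symptoms while they are tested off medication. Shortly after that paragraph comes the commitment: "Individuals will be asked about side effects at each visit and encouraged to share information about subjective changes".

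**When those risks arise.** Section 6.6 places the off-medication state at both the pre- and post-intervention visits. Section 6.8 places scans before and after the intervention. Section 6.4c makes both scans a condition of entry for the Parkinson group.

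**The concern.** The commitment in Section 12 and the operative schedule do not agree. Sections 6.6.5b and 10 and Table 2 are consistent with one another, and all three are narrower than Section 12. Site staff will work from Table 2 and the form, so the narrower window is the one that will be carried out.

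The narrower window suits events emerging under stimulation, but the two risks that Section 12 singles out beyond boredom and confidentiality come from scanning and from the off-medication state. At least half of the occasions on which those can occur lie outside the window. A hearing complaint after the first scan, or a bad off-medication baseline, would have no scheduled point at which it is asked about on the form, reviewed or passed on.

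Two features make such a gap hard to see afterwards. Section 6.6 says that a Parkinson participant who is too uncomfortable off medication may take it and is then withdrawn; if that happens at baseline, the participant never reaches a log. Section 10 sends no monthly summary when nothing has been reported, so silence about these procedures cannot be told apart from not having asked.

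**Working it through.** The protocol states no figure to reproduce. The check sets the timing of each named-risk occasion against the timing of the log.

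**Inputs**
- Log window: opens with the first intervention session and closes at the follow-up session (Section 6.6.5b; Table 2; Section 10).
- Off-medication occasions: 2 per Parkinson participant, baseline and follow-up (Section 6.6).
- Scans: 2 per scanned participant, one on each side of the intervention (Section 6.8); mandatory in the Parkinson group (Section 6.4c).
- Parkinson participants: 40 planned (Section 6.2).

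**Occasion by occasion**

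| Occasion | Who | Relative to the log | Covered? |
|---|---|---|---|
| Off-medication baseline | Parkinson | Before the first session | No |
| Pre-intervention scan | Parkinson; other scanned participants | Before the first session | No |
| Off-medication follow-up | Parkinson | At the last log | Yes |
| Post-intervention scan | Parkinson; other scanned participants | Not fixed by the text | No if after the follow-up log; yes if before it |

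The log completed at the first session does not rescue the first two rows. Its prompts concern that session and the interval since the preceding intervention session, and at session one there is no preceding session. The overall window also begins with the intervention.

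The last row is open. Table 2 puts Post-MRI in the final column, after Follow-up. Section 9 lists no separate MRI visit, treats the scan as extra time at the baseline visit, and describes the post-treatment assessment as the same as baseline. A scan done before the follow-up log is completed is therefore compatible with the text. Both orders are carried through.

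**Counts**
- Occasions per Parkinson participant: 2 off-medication visits + 2 scans = 4. For the group: 40 × 4 = 160.
- Post-intervention scan after the last log: 3 of 4 uncovered; 40 × 3 = 120 of 160 (75%).
- Post-intervention scan before the last log: 2 of 4 uncovered; 40 × 2 = 80 of 160 (50%).
- Any other scanned participant: 2 of 2 uncovered in the first case, 1 of 2 in the second. No group total is possible, because the protocol does not say how many non-Parkinson participants will be scanned.

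These are occasions on which a named risk may arise, not events. They assume that all 40 Parkinson participants complete both off-medication visits and both scans.

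**The case against.** **An intervention log may reasonably start with the intervention.** This is a legitimate choice for events emerging under stimulation, and taken alone it would not be an error. It becomes a problem because Section 12 names risks of study procedures outside the intervention and says that side effects will be asked about at each visit.

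**Section 12 might mean intervention visits only, or an informal verbal question.** Either is possible. However, the sentence closes the risk section, comes shortly after the off-medication paragraph, and concerns unknown risks of taking part in the study, so the wider meaning is the natural one. If the question is only verbal, its answers before the first session have no form and no place in the review schedule of Section 10.

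**Off-medication harm is managed and partly visible.** Section 6.6 provides for close monitoring, and a participant who has to take medication appears as a withdrawal. That stands, but monitoring does not record adverse events, and a withdrawal count omits anything milder.

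**A reader might infer that the safety comparison is confounded**, because off-medication symptoms at follow-up could be logged as arising since the intervention began with nothing earlier to compare them with. The documents do not support this. Parkinson participants are randomized 1:1 to real or sham (Section 7.2.a) and both arms are tested off medication, so such symptoms should arise in both. The UPDRS, Grooved Pegboard and gait and balance measures are taken off medication before and after the intervention (Sections 6.6 and 6.6.6; Table 2), which supplies a motor reference. The log also asks about severity, duration and possible relation to the intervention.

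**A reader might also infer that these procedures are never asked about at all.** That goes too far: the follow-up off-medication visit is covered, and the post-intervention scan may be.

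**Conclusion.** The contradiction is real and should be resolved. The off-medication Parkinson baseline and the pre-intervention scan lie outside the Adverse Events Log and its review however the text is read. Whether the post-intervention scan does too depends on taking Table 2's column order as the visit order, which nothing else in the protocol confirms. The result is therefore a range: half to three quarters of the named-risk occasions in the Parkinson group, and one or both scans for anyone else who is scanned. A single figure at either end would claim more than the text allows.

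The consequence is incomplete capture of harms from procedures that the protocol itself lists as risks, and a statement about safety questioning that the schedule does not deliver. The efficacy analyses and the active-versus-sham comparison are not threatened.

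**What to change.** Reconcile Sections 6.6.5b, 10 and 12 and Table 2:

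1. In Section 6.6.5b, let the recall window run from consent, or from the previous visit, instead of from the start of the intervention.
2. In Table 2, mark the log at Baseline, Pre-MRI and Post-MRI as well. For the second scan, an equivalent is to state that the last log is completed after it. Either way, say where that scan falls relative to follow-up.
3. In Section 10, extend both the review sentence and the IRB reporting sentence to the added visits.
4. Optionally, record medication state on the log for Parkinson participants, so that entries made off medication can be recognized as such.

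Narrowing the sentence in Section 12 would also remove the contradiction, but would leave the capture gap in place.

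The cost is a wording amendment, a few minutes of an existing form at visits that already take place, and more minor events to list. No treatment, schedule of stimulation or clinical rule changes.
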